This study is a preliminary randomized control trial evaluating a 9-week diet and lifestyle intervention on quality of life, patient-reported symptoms, and biomarkers associated with methylation. We will recruit forty-eight participants with 24 randomized to each study group. Refer to Figure 1 for an overview of the study flow.

Figure 1. Study Flow Overview

D.2 Study Intervention

Study participants will be randomized into an intervention or control group. The intervention group will undergo a 3-week washout period following the discontinuation of any non-medically required nutrition or herbal supplements. The intervention group will follow detailed diet and lifestyle recommendations over a 9-week period. Two webinars at the start of the

Protocol

Study Title: Methylation Diet and Lifestyle (MDL) Study

PI: [name], ND, MPH and [name], ND

IRB #: RB100217

Approval Date: 2.9.18

Ver. 1.1

intervention phase will provide information to participants on proper food and exercise choices, as well as how to access and use the required electronic resources (apps).

The control group will undergo the same testing measures as the intervention group, but will not have access to the education information or be instructed to change diet or lifestyle factors. They will have access to the information after the study is complete.

D.2.1 Diet Recommendations

Specific dietary guidelines will be outlined for participants and should include the following:

Per week	Per day

3 servings of liver
 
 • (1 serving = 3 oz) • Choose preferably organic liver 
5-10 eggs
 
 • Ideally free-range, organic, omega-3 enriched 	
2 cups of dark leafy greens
 
 • Measured raw, chopped, and packed • Including kale, Swiss chard, collards, spinach, dandelion, mustard greens • Does not include salad greens such as romaine, iceberg, Spring mix 
2 cups cruciferous vegetables
 
 • Measured raw, chopped, and packed • Including broccoli, cabbage, cauliflower, Brussels sprouts, bok choy, arugula, kale, watercress, rutabaga, kohlrabi, radish, turnip
General	

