Not all foods recommended and consumed during the study intervention may be captured by VioScreen. An additional food frequency questionnaire (FFQ), with approximately 250 foods and beverages, was created to assess consumption. It has been designed to be consistent with the validated block Brief FFQ by NutritionQuest. This will be administered electronically via RedCap online database to all study participants at Visits 1, 2, and 3.

D.2.7.5. Adherence phone calls

Participants will be contacted via phone once per week during the first 4 weeks of the study and every other week for the remainder of the study. Designated health coaches will assess for adherence to the study intervention including dietary, stress management, and exercise recommendations. Participants will be able to ask questions pertaining to the study intervention.

Refer to Appendix B for detailed script of these phone calls.

Protocol

Study Title: Methylation Diet and Lifestyle (MDL) Study

PI: [name], ND, MPH and [name], ND

IRB #: RB100217

Approval Date: 2.9.18

Ver. 1.1

D.3 Description of Participant Population

D.3.1. Participant Characteristics

Sample size: n=48

We will enroll and randomize up to 48 people which will allow for 20% attrition such that we have an evaluated sample size of 40 to allow for withdraws or dropouts.

Age: 50-72

Gender: Males only

Minorities: all racial and ethnic backgrounds will be recruited from the general population without preference or discrimination.

Vulnerable Populations (e.g. children, pregnant women, cognitively impaired): No vulnerable populations will be enrolled.

D.3.2. Inclusion and Exclusion Criteria

Individuals must meet the following participation criteria:

Inclusion criteria:

- Males, ages 50-72
- Willing to adhere to 9 weeks of a dietary and lifestyle program including specific nutrition and exercise guidelines
- Willing to avoid any over-the-counter medications, supplements or herbal products for the length of the study, except short-term use (<1 week) use at least 1 week before scheduled study visits
- Willing to have blood drawn three times and abstain from food or beverage intake for 10-12 hours before blood draws
- Willing to provide saliva samples
- Willing to track food intake, sleep, stress management techniques, and exercise daily
- Willing to drink a nutrient-enriched beverage and take a encapsulated probiotic daily
- Willing and able to use electronic devices and connect to the internet

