Once a participant is deemed eligible and provided signed consent, the study staff will determine randomization order using a random number generator (randomization.com). After enrollment, the study coordinator will select the next sequential envelope from the locked filing cabinet within the study site office. The study staff will write the current date and participant initials on the bottom right corner of the envelope and open the envelope and retrieve its contents. The envelope contents will show which cohort the participant is assigned to, with intervention or control. This will be assigned to the participant ID number and entered into REDCap.

D.5.7. Washout Period

Study participants assigned to the intervention group will be asked to refrain from taking any over-the-counter supplements, medications or herbal products, except short-term use (<1 week) and at least 1 week before scheduled study visits, alcohol, nicotine, marijuana or cannabinoids (including CBD products) or recreational drugs/substances for 3 weeks before the baseline visit. Written instructions will be provided.

D.5.8. Study Visits

There will be 3 in-person study visits for all participants during the 9-week study.

Baseline/Study Visit 1 (Week 1)

The following procedures, evaluation and/or assessments will be obtained at Study Visit 1:

- Height and weight
- Vital signs including heart rate, blood pressure, respiration rate and temperature

Protocol

Study Title: Methylation Diet and Lifestyle (MDL) Study

PI: [name], ND, MPH and [name], ND

IRB #: RB100217

Approval Date: 2.9.18

Ver. 1.1

- Questionnaires including Lifestyle Habits, PROMIS-29, MYMOP, MSQ, and NUNM Adverse Events, VioScreen
- Blood draw to collect 2 tubes of blood
- Finger stick to collect 5 drops of blood
- Saliva sample
- If in intervention group, will receive study supplements for first 4 weeks and instructions on how and when to take
- Case report form completed by study staff
- Waist-to-hip ratio will be calculated using the following methods:
 - Participant with stand up straight and breathe out. Use a tape measure to check the distance around the smallest part of the waist, just above the umbilicus. This is the waist circumference.
 - Measure the distance around the largest part of the hips — the widest part of the buttocks. This is the hip circumference.
 - Calculate the waist-to-hip ratio by dividing the waist circumference by the hip circumference.

Study Visit 2 (Week 5)

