- The Principal/Clinical Investigator decided that withdrawal/discontinuation was in the best interest of the participant due to an adverse event, non-compliance, or another reason
- The participant requests withdrawal from the study for reasons other than above
- The participant failed to return for study visits

If a participant withdraws before the second visit, they will be replaced, however participants who withdraw between the second and third visits will not be replaced. Every effort will be made to collect a final salivary sample and all final labs from all participants, even if they withdraw from the study early.

D.7. Study Products

D.7.1. PhytoGanix (tropical fruit flavor)

Organic Superfruits & Greens Powder Drink Mix is a food-based phytonutrient blend designed to support intestinal health and immune function.

Protocol

Study Title: Methylation Diet and Lifestyle (MDL) Study

PI: [name], ND, MPH and [name], ND

IRB #: RB100217

Approval Date: 2.9.18

Ver. 1.1

Serving Size: 1 Scoop (10.4 grams)

Ingredient	Amount per serving
Calories	40
Total Carbohydrate	9 g
Dietary Fiber	1 g
Sugars	1 g
Protein	1 g
Vitamin C (as ascorbic acid)	100 mg
Calcium	20 mg
Iron	1.4 mg
Sodium	30 mg
Organic Seed and Prebiotic Blend:	5.53 g
Isomalto-Oligosaccharide, Flax Seed Powder, Chia Seed Powder, Quinoa (Chenopodium quinoa Willd.) Sprout Powder	
Organic Veggie Blend:	2.35 g
Spirulina Whole Algae Powder, Carrot Root Powder, Broccoli Head Powder, Cauliflower Head Powder, Spinach Leaf Powder, Parsley Leaf Powder, Bamboo Shoot Extract, Beet Root Powder	
Organic Fruit Blend:	1.2 g
Apple Fruit Powder, Pineapple Fruit Powder, Strawberry Fruit Powder, Raspberry Fruit Powder, Blackberry Fruit Powder, Blueberry Fruit Powder	
Herbal Support Blend:	300 mg
Milk Thistle Seed Extract, Turmeric Rhizome Extract, Green Tea Leaf Extract, Reishi Mushroom Whole Plant Powder, Maitake Mushroom Whole Plant Powder, Shiitake Mushroom Whole Plant Powder, Japanese Knotweed Root Extract, Quercetin Dihydrate, Organic Maca Root Powder, Organic Cassia Bark Powder, Dong Quai Root Powder, Ginger Root Powder, Garlic Bulb Powder	
Enzyme Blend (including protease, amylase, lipase, and cellulase)	200 mg
Lactobacillus acidophilus VK3 Strain	200 mg

Protocol

Study Title: Methylation Diet and Lifestyle (MDL) Study

PI: [name], ND, MPH and [name], ND

IRB #: RB100217

Approval Date: 2.9.18

Ver. 1.1

D.7.2. UltraFlora Intensive Care

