Study Title: Methylation Diet and Lifestyle (MDL) Study

PI: [name], ND, MPH and [name], ND

IRB #: RB100217

Approval Date: 2.9.18

Ver. 1.1

is a secure, web-based application that supports electronic data capture for research studies. REDCap features include: 1) intuitive data entry features; 2) audit trails for tracking data manipulation and export; 3) user-based privileges that support HIPAA compliance; 4) seamless data export to common statistical packages; and 5) procedures for importing data from external sources. The REDCap database will be accessible only by the study team. Data will be destroyed 3 years after completion of the study. Computer files will be deleted from the server and paper files will be destroyed using a professional document shredding service.

All completed forms will be kept in locked files to which only project personnel have access. These files will also be in locked rooms. Data from paper forms will be manually entered into REDCap and kept as electronic files. Electronic files will be password protected with access given to study personnel only. All analyses will be conducted by study staff at the Helfgott Research Institute. The study biostatistician will only access de-identified data exported from REDCap to Excel or SPSS. Only de-identified data will be presented in any reports, presentations or manuscripts.

G.2. Informed Consent

Consent will be obtained from the participants for the study protocol. The Consent Form will include the purpose of the study, a description of the procedures, a list of risks and benefits, an assurance of confidentiality, an assurance of withdrawal without prejudice, study incentives, and telephone numbers for answering questions about the research. Participants will also be given information on their right to privacy for personal health information based on HIPAA regulations. Procedures for data sharing using de-identified data will be explained.

G.3. Adverse Event Monitoring

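### Section D.5.6 has study staff set the randomisation order after consent yet draws from pre-filled envelopes, and it does not separate list-maker from enroller, so allocation is not securely concealed

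*Protocol*

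**What the plan says.** Protocol D.5.6 gives the procedure in this order:

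1. After a man has been found eligible and has consented, "the study staff will determine randomization order using a random number generator (randomization.com".
2. After enrolment, "the study coordinator will select the next sequential envelope from the locked filing cabinet within the study site office".
3. Study staff put the date and the man's initials on the envelope and open it. The arm is recorded against his ID in REDCap.

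The section names no block scheme or other restriction, does not describe the envelopes as sealed or opaque, and names nobody independent of enrolment as maker of the list.

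Three other places bear on it. D.1 says: "We will recruit forty-eight participants with 24 randomized to each study group". D.3.1 says: "We will enroll and randomize up to 48 people which will allow for 20% attrition", so that "we have an evaluated sample size of 40 to allow for withdraws or dropouts". D.6 says: "If a participant withdraws before the second visit, they will be replaced". It does not say how the replacement's arm is decided.

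On context, enrolment is rolling (D.5.3), randomisation follows the screening visit (D.5.1), the control group is wait-listed (D.2.6) and the primary outcome is the self-reported PROMIS-29 (D.4.1).

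**The concern.** The procedure cannot be carried out as written, because its first step and its envelopes belong to two different schemes. Under either scheme, the text leaves open whether the people who enrol a man can know or influence his arm.

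That matters more here than in a blinded trial. At the screening visit each man samples the study drink and is asked whether he will take it twice a day (D.5.4), so staff can form a view of his motivation before allocation. Everyone knows the arm afterwards, and the primary outcome is the man's own report. PROMIS-29 is first collected at Visit 1 (Table 4), after randomisation and, in the intervention arm, after the three-week washout. There is no pre-allocation score on the primary outcome against which selective assignment could be checked.

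Two smaller issues go with it. Nothing stated guarantees 24 per arm. And if a replacement simply takes the leaver's arm, his allocation is known before he is enrolled.

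**Working it through.** **The plan's own figure.** 40 evaluable × 1.20 = 48, which splits into 24 + 24. (Inflating by division gives 40/0.80 = 50, and 48 × 0.80 = 38.4. That is a separate matter and is not relied on here.) The protocol gives no alpha, power, effect size or SD for the sample size, so nothing more of it can be reproduced.

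**The sequence of steps.** D.5.6 allows two readings.

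- *The list exists beforehand and step 1 is loosely worded.* The envelopes then make sense. But those who made the list know future assignments, and a locked cabinet does not hide a list from its makers. Whether they also screen or enrol is not stated.
- *The order really is generated after each consent.* Nobody can then foresee it while judging eligibility. But the envelopes have no function, and nothing stated prevents a draw from being repeated.

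Neither reading gives a stated separation between making the list and enrolling.

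**Arm sizes, if randomisation were simple (assumption).** With X ~ Binomial(48, 0.5):

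- P(24:24) = C(48,24)/2^48 = 0.1146, or 11.5%.
- P(28:20 or worse) = 2 × P(X ≥ 28) = 0.3123, or 31.2%.
- P(30:18 or worse) = 2 × P(X ≥ 30) = 0.1114, or 11.1%.

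**Cost of imbalance.** Relative efficiency = 4·n1·n2/N². Power = Φ(d/√(1/n1 + 1/n2) − 1.96), with an assumed standardised effect d = 0.81, two-sided 5%, all 48 analysed.

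| Split | Relative efficiency | Power |
|---|---|---|
| 24:24 | 100% | 80.1% |
| 20:28 | 4 × 20 × 28/2304 = 97.2% | 79.0% |
| 18:30 | 4 × 18 × 30/2304 = 93.8% | 77.5% |

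With d = 0.5 the powers are 41.0%, 40.0% and 38.9%.

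**Guessing from past assignments.** Suppose staff know the past assignments and any block size, and always guess the arm with more places left. The expected share of correct guesses is then:

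| Scheme | Correct guesses | Known with certainty |
|---|---|---|
| Simple | 50% | 0% |
| One block of 48 | 58% | 4% |
| Blocks of 8 | 67% | 20% |
| Blocks of 4 | 71% | 33% |
| Blocks of 2 | 75% | 50% |

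A restriction that secures balance therefore makes guessing easier in an unblinded trial unless block sizes vary and are withheld. These figures concern guessing only. Someone who has seen the list knows the next arm under any scheme.

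**The case against.** The strongest reply is that D.5.6 does contain concealment steps: sequential envelopes, a locked cabinet, selection only after enrolment, and date and initials listed before opening. Eligibility and consent come first. The likeliest explanation of the timing sentence is loose drafting. Study staff is also a broad term: G.1 says that study staff at the institute do all analyses, so it could include the biostatistician. Roles are unspecified rather than shown to overlap. Detail on blocking is often kept outside the protocol on purpose, and a randomisation order is compatible with a permuted list of 24 + 24.

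Most of this stands, and it limits what may be concluded:

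- A reader might infer that allocation is predictable. The documents do not show that anyone who enrols knows the list.
- A reader might infer that randomisation is simple. It is not stated to be, and the silence does not prove it.
- A reader might infer that the arms will be both predictable and unequal. The two pull against each other, since simple randomisation leaves each next assignment at 50:50.
- A reader might put a size on the bias. Steering k men per arm who differ by 5 T-score points in expected change would shift the group difference by 2 × k × 5/24, or 0.8 to 1.7 points for k = 2 to 4. Neither k nor the 5 points has support in the protocol, so this is not carried into the conclusion.
- A reader might infer that tampering could never be found. Dated, initialled envelopes, REDCap audit trails (G.1) and sponsor monitoring (G.6) permit sequence checks, although they would not reveal knowledge of the list.

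What the reply does not remove is the conflict of steps within D.5.6 and the lack of any stated separation of roles. These are defects in a procedure that the protocol does set out.

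**Conclusion.** The point holds in limited form. D.5.6 contradicts itself on when the order is made, and it assigns the making of the order and the opening of envelopes to study staff without separating list-maker from enroller. Concealment is therefore not secured, in a design that is exposed to selection bias because it is unblinded with a self-reported primary outcome. No bias has been demonstrated, and its size cannot be derived from the documents.

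The absence of a stated restriction behind the 24 per arm is secondary. The 11.5% and 31.2% rest on assumed simple randomisation. Even then, a 28:20 split lowers power by only about one percentage point (80.1% to 79.0% at the assumed effect of 0.81). The replacement rule in D.6 needs an allocation method that fits the ceiling of 48 in D.3.1.

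**What to change.** Amend D.5.6 as follows:

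- Delete the sentence that has study staff determine the order after consent.
- State that the whole list is generated before the first enrolment by the study biostatistician, or by another existing team member with no part in screening, enrolment or envelope opening. G.1 says of the biostatistician: "The study biostatistician will only access de-identified data exported from REDCap to Excel or SPSS". That limits data access and does not by itself establish absence of participant contact, so the amendment should state the separation. Making the list needs no identified data.
- Use permuted blocks of varying size, with the sizes withheld from site staff. If the first 48 envelopes are to hold exactly 24 per arm, the block sizes must sum to 48 at that point.
- Have the same person prepare sequentially numbered, opaque, sealed envelopes. Keep the dating and initialling before opening.
- Extend the list beyond 48, and state in D.6 that a replacement is randomised from the next envelope and not placed in the leaver's arm. Reconcile this with the ceiling of 48 in D.3.1, and accept that final arm sizes may differ slightly from 24:24.

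The cost is about an hour of an existing team member's time, one rewritten paragraph, and matching edits in D.3.1 and D.6. Sample size, visits and analysis are unaffected, apart from any replacements that take the number randomised past 48.

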- Able to speak, read and understand English

Exclusion criteria:

- Currently taking any of the following prescription medications
 - Proton pump inhibitors: omeprazole (Prilosec, Prilosec OTC); aspirin and omeprazole (Yosprala); lansoprazole (Prevacid, Prevacid IV, Prevacid 24-Hour); dexlansoprazole (Dexilent, Dexilent Solutab); rabeprazole (Aciphex, Aciphex Sprinkle); pantoprazole (Protonix)

Protocol

Study Title: Methylation Diet and Lifestyle (MDL) Study

PI: [name], ND, MPH and [name], ND

IRB #: RB100217

Approval Date: 2.9.18

Ver. 1.1

- H2-blockers: nizatidine (Axid, Axid AR, Axid Pulvules); famotidine (Pepcid, Pepcid AC); cimetidine (Tagamet, Tagamet HB); ranitidine (Zantac)
- These classes of medications are excluded due to direct (due to nutrient requirements for metabolism) and indirect (through impaired digestion and assimilation of nutrients).
- Use of nutrition supplements or herbal products not prescribed by a licensed healthcare provider for a medical condition
- Currently following a prescribed dietary/lifestyle program or initiate within the 30 days prior to baseline
- Initiation of or changes to an exercise regimen within 30 days prior to baseline
- Use of nicotine, marijuana or cannabinoids (including CBD products) or recreational drugs/substances (such as but not limited to cocaine, phencyclidine [PCP], and methamphetamine) current/within the last 30 days or use during the study
- Have a diagnosis of cardiovascular disease, kidney disease, liver disease, diabetes, autoimmune disease, high blood pressure, or cancer (does not include *basal cell carcinoma, squamous cell carcinoma, and/or carcinoma in situ of the cervix*).
- Have a diagnosis of an immunodeficiency condition, such as Human Immunodeficiency Virus (HIV) infection or Acquired Immune Deficiency Syndrome (AIDS)
- Have a diagnosis of neurodegenerative conditions such as, amyotrophic lateral sclerosis (ALS), Parkinson’s disease, Multiple Sclerosis, or Alzheimer’s disease.
- Excessive alcohol consumption (more than 4 drinks per day or 14 per week on average)
- Known sensitivity, intolerance or allergy to ingredients in the study supplements or in the recommended dietary therapy
- Currently receiving intravenous nutrient therapy
- Currently participating in another interventional research study or participated in another interventional study within the last 3 weeks prior to baseline

D.4 Outcome Measures

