Study Title: Methylation Diet and Lifestyle (MDL) Study

PI: [name], ND, MPH and [name], ND

IRB #: RB100217

Approval Date: 2.9.18

Ver. 1.1

D.5 Participant Schedule

D.5.1 Overview

Individuals will be screened over the phone and at one in-person visit. Eligible participants who choose to enroll in the study will attend a total of 4 in-person visits. Participants will be randomized into either the intervention or control group after the screening visit. All study visits will be conducted at the Helfgott Research Institute in Portland, OR. Refer to Table 4 for an outline of the study visits.

Table 4: Study Procedures

	Phone Screening	Screening Visit	Study Visit 1 (Week 1)	Study Visit 2 (Week 5)	Study Visit 3 (Week 9)
Eligibility screening	X				
Consent for study participation		X			
Eligibility verification		X			
Demographic form		X			
W-9		X			
Anthropometrics/Vitals: height, weight, waist-hip ratio, heart rate, blood pressure, temperature, respiratory rate		X	X	X	X
Questionnaires: 
 • NUNM Multi-system Symptom/Adverse Event • MSQ • MYMOP • PROMIS-29 • Lifestyle Habits • VioScreen • Study specific FFQ 			X	X	X
Blood Draw, blood spot card and saliva sample			X	X	X

Protocol

Study Title: Methylation Diet and Lifestyle (MDL) Study

PI: [name], ND, MPH and [name], ND

IRB #: RB100217

Approval Date: 2.9.18

Ver. 1.1

DNA Methylation Pathway Profile - SNP Panel			X		
Infinium Methylation EPIC Index			X		X
Methylation Profile			X	X	X
Folate Vitamer Panel			X	X	X
Estimated Time to Complete	15 minutes	45 minutes	90 minutes	90 minutes	90 minutes

D.5.2. Recruitment

Recruitment will be conducted in the general community surrounding Portland, OR using flyers, online, newspaper, and electronic newsletters.

D.5.3. Telephone Screening

Potential participants will be screened over the phone prior to coming in for the first visit. A standardized telephone script will be used. The telephone screening call will take approximately 10-15 minutes. Participants who meet eligibility criteria over the phone will be scheduled for a screening visit. The consent form will be provided to participants prior to the screening visit via email; they will be instructed to review the form ahead of time but not to sign it until the screening visit where they can ask questions about the study. If an individual is eligible for the study, enrollment will happen on a rolling basis.

D.5.4. Screening Visit

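### The 3-week pre-baseline washout is given to the intervention arm only, after allocation is known, so the reference visit for the primary analysis is measured after randomisation under conditions that can differ by arm

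*Protocol*

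**What the plan says.** **Allocation.** Protocol D.5.1: "Participants will be randomized into either the intervention or control group after the screening visit". Under D.5.6 the envelope is opened once eligibility and consent are complete, and its contents show the arm.

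**Washout.** D.5.7 addresses one arm: "Study participants assigned to the intervention group will be asked to refrain from taking any over-the-counter supplements, medications or herbal products". The list goes on to alcohol, nicotine, cannabis and "recreational drugs/substances for 3 weeks before the baseline visit". D.2 says the same independently: "The intervention group will undergo a 3-week washout period following the discontinuation of any non-medically required nutrition or herbal supplements".

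**Controls.** D.2 gives them the same tests but says they "will not have access to the education information or be instructed to change diet or lifestyle factors". No washout is mentioned for them.

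**Criteria that apply to both arms (D.3.2).** Participants must be "Willing to avoid any over-the-counter medications, supplements or herbal products for the length of the study", with an exception for short-term use that ends at least a week before a scheduled visit. Among the exclusions is "Use of nutrition supplements or herbal products not prescribed by a licensed healthcare provider for a medical condition". Nicotine, cannabis and recreational drugs within the last 30 days or during the study also exclude. Alcohol is restricted only at the level "Excessive alcohol consumption (more than 4 drinks per day or 14 per week on average".

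**Measurement and analysis.** Table 4 schedules no questionnaire, blood or saliva sample before Visit 1. Under D.4.1 the PROMIS-29 domains look back 7 days, except Physical Function, which has no set time frame. G.4 tests Group*Visit in a random-intercept mixed model and reports contrasts of change from baseline to Weeks 5 and 9.

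**The concern.** A change-from-baseline comparison is protected by randomisation only if baseline is measured before allocation can affect it. Here one arm is told to change its behaviour for 21 days, and everyone may know their arm, before the first self-reported outcome is taken. A Visit 1 difference caused by that instruction goes straight into the primary contrast. If the washout makes the intervention arm feel worse at Visit 1, recovery from it looks like benefit. If it makes them feel better, a real benefit is partly hidden.

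No outcome is collected before randomisation, so no later analysis can recover a clean baseline.

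**Working it through.** The plan states no figure on this point, so there is nothing to reproduce. The check has two parts: what can differ between arms, and what a difference would do.

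**1. Sequence.** Screening and consent → envelope opened → 3-week washout (intervention arm only) → Visit 1 with first measurement of every outcome → introductory webinar and start of supplements (D.7.3). In the intervention arm the 7-day PROMIS-29 window at Visit 1 lies wholly inside the 21-day washout.

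**2. What can differ before Visit 1, item by item**

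| Item in the D.5.7 list | Already restricted in both arms by D.3.2? | Difference that remains |
|---|---|---|
| Nicotine, cannabis, drugs | Yes: 30 days and during the study | Little or none |
| Supplements, herbal products | Yes, if the exclusion is strictly applied | None; but D.2 describes stopping such products, which implies that users may enrol. On that reading they differ |
| Over-the-counter medication | Partly: for the length of the study, no 3-week pre-baseline period | Can differ, chiefly in the earlier washout weeks |
| Alcohol | Only above the excess limit | Differs by instruction |

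An eligible man may average up to 14 drinks a week, so alcohol before Visit 1 can differ by up to about 3 × 14 = 42 drinks per man. This ceiling rests on an average limit. It measures exposure, not T-score points.

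The exploratory folate and methylation biomarkers are exposed through supplements only if D.2 overrides the D.3.2 exclusion.

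**3. Bias.** Let b be the between-arm shift at Visit 1 caused by the washout, and f the share of it still present at Weeks 5 and 9. Then

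bias of the Week 9 change contrast = b(1 − f) in size.

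It is b if f = 0 and zero if f = 1. Full persistence cannot be assumed: D.5.7 asks for abstinence only up to the baseline visit, and D.2.1 does not mention alcohol.

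**4. Effect on the test (illustration).** The protocol gives no SD, correlation or alpha. Assumed: alpha 0.05 two-sided, one T-score, SD 6, 8 or 10, correlation between visits ρ = 0.6, no true effect. The 40 evaluable participants (D.3.1) are taken as n = 20 per arm. With arm differences d = (b, fb, fb) over the three visits, the Group*Visit test is a noncentral F with 2 and 76 df and

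λ = n·Σ(d_t − d̄)² / [2·SD²·(1 − ρ)].

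Example: b = 2, f = 0, SD 8. d = (2, 0, 0), d̄ = 0.667, Σ = 1.778 + 0.444 + 0.444 = 2.667, so λ = 20 × 2.667 / (2 × 64 × 0.4) = 1.04. The rejection rate is 13.3%; a 20,000-run simulation gave 13.1%.

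False-positive rate of Group*Visit for SD 6 / 8 / 10:

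| b (points) | f = 0 | f = 0.5 | f = 1 |
|---|---|---|---|
| 1 | 8.5 / 6.9 / 6.2% | 5.8 / 5.5 / 5.3% | 5% |
| 2 | 20.5 / 13.3 / 10.1% | 8.5 / 6.9 / 6.2% | 5% |
| 3 | 41.6 / 25.0 / 17.3% | 13.3 / 9.5 / 7.8% | 5% |

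The Week 9 contrast alone (38 df; SE = SD·√(2(1 − ρ))·√(2/n) = 1.70 / 2.26 / 2.83) gives nearly the same: 21.0 / 13.8 / 10.6% for b = 2, f = 0.

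The figures depend on ρ. For b = 2, f = 0, SD 8 the Group*Visit rate is 10.4% at ρ = 0.4 and 22.6% at ρ = 0.8.

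**The case against.** The strongest reply is that the arms differ less than D.5.7 suggests. Most of its list already binds both arms through D.3.2. The over-the-counter criterion can even be read as barring use in the week before any scheduled visit, Visit 1 included, and that week is the PROMIS-29 window. On that reading alcohol is the main difference left inside the window. Whether abstinence from alcohol continues after baseline may be settled in Appendix A, which is not at hand; if it does continue, the bias moves towards zero.

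The shifts of 1 to 3 points are assumed. At b = 0.5 and f = 0 the Group*Visit rate is 5.3–5.8%, close to nominal. At ρ from 0.4 to 0.8 the rate for b = 3, f = 0 runs from 13% to 72%, so no single range should be relied on. G.4 reports group means at each visit, so a large Visit 1 gap would be visible, and between-arm comparisons at Weeks 5 and 9 that do not use baseline remain protected by randomisation.

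Most of this stands as a limit on size. It does not remove the point. Alcohol and over-the-counter use in the earlier washout weeks still differ by instruction, a visible Visit 1 gap could not be told apart from chance, and the analysis that G.4 specifies does use Visit 1. Nor does it help to call the washout part of the intervention: a baseline taken after it would leave its effect out of the change score.

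**Conclusion.** The concern holds, and the protocol should be changed. From the text alone it is certain that the arm is revealed before the washout, that the washout is stated for one arm in two sections, and that no outcome is measured before Visit 1, the reference for the primary test. It is not established that baseline values will differ; the documents show only that the conditions can. The size, direction and persistence of any shift are unknown, and no document supports a particular b. The false-positive rates rest on the assumed SD, correlation, shift and 20 per arm, and serve to show that a shift of 2 or 3 points that fades would matter in a trial of this size. The conflict between D.2 (supplements are stopped) and D.3.2 (their users are excluded) decides whether the exposure reaches the biomarkers.

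**What to change.** Open the allocation envelope at the end of Visit 1, after the baseline questionnaires and samples, so that any pre-baseline instruction is the same for everyone. If allocation has to stay after screening, give both arms the same pre-baseline instruction. Either change sets b = 0 as far as the instruction is concerned; the first also keeps knowledge of the arm out of the baseline answers. Reconcile D.2, D.3.2 and D.5.7 on whether supplement users can enrol and on who stops what. What is stopped and for how long is for the investigators to decide; it should not differ by arm before baseline.

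The cost is a protocol amendment to D.2, D.5.1, D.5.6 and D.5.7, and to D.3.2 if the reconciliation requires it. Logistics barely change, because supplements are first handed out at Visit 1 and started only after the introductory webinar. The downside is that future controls would follow a pre-baseline instruction that is partly new to them: the inclusion criterion covers over-the-counter products for the length of the study, but not alcohol or a 3-week period before baseline.
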